#### **10.4** Significance Testing

A 5% level test will be used for the analysis of the primary endpoint comprised of 2 pairwise 2.5% level one sided tests of the two buprenorphine arms versus the no-buprenorphine arm.

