#### 2.7 Analyses

The primary endpoint is the number of cocaine use days during the 30-day evaluation period (the final 30 days of active medication administration prior to taper; days 25-54). This will be analyzed using appropriate statistical methods for the intent-to-treat and evaluable samples. Statistical tests will be two one-sided 2.5% level tests contrasting buprenorphine-containing regimens versus the control (no buprenorphine) for an overall experimentwise 5% Type I error rate. Other analyses will include summaries of the characteristics of the participants in each condition. Analyses will address abstinence, reduction in drug use, treatment retention, and treatment completion.

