#### **10.2** Rationale for Sample Size and Statistical Power

The study has been designed to include 300 individuals randomly assigned at a 1:1:1 ratio to the 3 treatment arms. The sample size was developed from a simulation study of the anticipated trial characteristics considering the number of abuse days, withdrawal probabilities, probability of underreporting abuse and effect size. Prior studies of a similar population (NIDA CTN-0007 Motivational Incentives for Enhanced Drug Abuse Recovery: Methadone Clinics) indicates that in a thirty day period, participants had about 9 cocaine abuse days, with a standard deviation nearly the size of the mean (mean=9.5, sd=8.5). The endpoint of this study is the number of cocaine use days during the 30 day evaluation period. Absent a treatment effect, it is assumed that each individual's daily use follows a Bernoulli distribution, but that individual's use risk varies, with sufficient population variability to match the anticipated extra-binomial variability noted from the prior study. Specifically a beta-binomial distribution is assumed for daily use with parameters (b1= .45, b2=1). Since the mean of the beta binomial is b1/b1+b2, then the expected number of use days in a 30 day period is 9.31 and the standard deviation is 9.08.

While verification of some daily reports will be substantiated with urine testing, underreporting of use may occur. We anticipate that this underreporting may vary among individuals. In the simulation underreporting of use is modeled under assumptions of complete accuracy (0% underreporting), 20% underreporting and 40% underreporting of use days. Conditional on use, the probability of underreporting is modeled with a beta-binomial distribution with parameters of (.2, .8) for the 20% level and (.4, .6) for the 40% level.

Losses to follow-up are assumed to occur in 5% of the participants prior to initiation of the evaluation period. In addition, a daily loss probability is presumed that is scaled by the individuals mean use probability from the initial beta-binomial distribution. Thus, individuals with higher use rates are more likely to discontinue. In the simulation, the unscaled daily probability is set at .008 and this results in an 18% dropout rate during the evaluation period.

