The test statistic used in the simulation is a nonparametric test (Wilcoxon) comparing use-free days in the 2 active treatment arms using an experimentwise 5% Type 1 error from performing 2 pairwise tests of the buprenorphine arms versus control each at the 2.5% one-tailed level. In individuals who withdraw during the evaluation period, the score is the percentage of use-free days during the completed period scaled up for the entire 30-day observation period. Note that

the simulation utilized the number of use-free days as the endpoint, however, this analysis is comparable to one in which the endpoint is defined as number of use days.

Note that an alternative statistic, the t-test, was examined in the simulation but power was consistently less (and on the order of 20 percentage points less) for several key situations. Simulated power was also less when analyzing the main effect from a repeated measurement linear model.

Under these assumptions, the following results were obtained with the randomized sample size of 300 (i.e. 100/arm) and 1,000 replications of each condition.

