#### **10.3** Statistical Methods for Primary and Secondary Outcomes

The primary endpoint will be analyzed with the 2 sample Wilcoxon statistic.

The rich data set will permit a series of additional analyses addressing secondary objectives 1-10. Safety analyses are outlined in Section 10.9. The Treatment Effectiveness Score (TES) (Ling et al. 1997) is the percentage of the scheduled urine drug screens that were both provided and negative. TES will be evaluated during the evaluation period for both cocaine and opioid use. Simple contrasts of the treatment arms will be performed with the Wilcoxon statistic. Additional analyses will examine the primary endpoint adjusting for strata and other covariate effects including gender, age and race. Repeated-measurement analysis models will be used to explore presence of time-related treatment effects, including severity of cravings and level of mood disturbance. Additional analyses will include assessment of treatment effect in the preevaluation period (Days 1-24), over the course of the entire treatment period and during the follow-up period. Changes occurring over the treatment period in severity and type of drugrelated problems and in quality of life will be summarized and compared between treatment groups using the two sample Wilcoxon test for continuous outcomes or the chi-square test or Fisher's Exact Test for categorical outcomes.

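### The fixed 2 × 2.5% split is valid, but a Holm step-down would raise the chance of showing both doses at the same one-sided 5% experimentwise error

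*Protocol*

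**What the plan says.** The protocol gives the decision rule in three places, and they agree.

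- Section 10.4: "A 5% level test will be used for the analysis of the primary endpoint comprised of 2 pairwise 2.5% level one sided tests", each comparing one buprenorphine arm with the no-buprenorphine arm.
- Section 2.7 describes the same pair of one-sided tests "for an overall experimentwise 5% Type I error rate".
- Section 10.2 bases the power simulation on "2 pairwise tests of the buprenorphine arms versus control each at the 2.5% one-tailed level".

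Section 10.3 names the test: "The primary endpoint will be analyzed with the 2 sample Wilcoxon statistic". Section 10.2 sets the size: "300 individuals randomly assigned at a 1:1:1 ratio to the 3 treatment arms". Section 10.5 plans one futility look per buprenorphine arm and no efficacy stop, and all type I error is spent at the end. No section provides a step-down, an ordering of the doses or any passing of alpha from one test to the other. Section 12.7 says the final analysis follows the protocol's own analytical section.

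**The concern.** An equal fixed split (Bonferroni) holds the experimentwise error at 5%, but it stays at 2.5% for the second dose even after the first has been rejected. From that point only one null hypothesis can still be falsely rejected, so the whole 5% could be used on it. Holm's procedure does this: test the smaller p-value at 2.5% and, if it is rejected, test the other at 5%. It rejects everything the fixed split rejects, and sometimes more.

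What is at stake is the conclusion on the second dose. The trial randomizes two doses, and section 4.1.4 says it will provide dosing information. The power to show each dose, and to show both, is therefore of practical interest, and some of it is left unused at no saving in the declared error rate.

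**Working it through.** **Inputs from the protocol.** One-sided 2.5% per test and 5% experimentwise (2.7, 10.2, 10.4). Allocation 1:1:1 with 100 per arm (10.2). Pairwise power with no underreporting of .635, .886 and .974 for gains of 2.27, 3.16 and 3.94 days (table in 10.2).

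**1. Reproducing the plan's figures.**

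- Alpha: 0.025 + 0.025 = 0.05.
- Control distribution, beta-binomial (0.45, 1) over 30 days: mean = 30 × 0.45/1.45 = 9.31. Variance = 30 × 0.3103 × 0.6897 × (31.45/2.45) = 82.4, so SD = 9.08. The protocol says "the expected number of use days in a 30 day period is 9.31 and the standard deviation is 9.08".
- Power: section 10.2 does not say how treatment lowers use. Assuming that each daily use probability falls by 0.10, 0.15 or 0.20 (floored at 0), the mean gains are 2.27, 3.18 and 3.99 days. A simulation with 95 analysed per arm, the stated dropout model and a one-sided 2.5% Wilcoxon test gives .634, .896 and .982, against the stated .635, .886 and .974. Across all nine table cells, eight agree within 2 points. The ninth (3.16 days, 20% underreporting) differs by 2.4 points (.849 against .873).

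The table is thus consistent with the fixed 2.5% test.

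**2. Error rate.** With equal arms and a shared control, the two test statistics have correlation 0.5 under the null. Critical values are 1.960 (2.5%) and 1.645 (5%).

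- Fixed split, global null: 0.025 + 0.025 − P(both > 1.960) = 0.050 − 0.0046 = 0.0454.
- Holm, global null: a first rejection still needs a statistic above 1.960, so the figure is again 0.0454.
- Holm, one dose effective: the null dose can be rejected only if its statistic exceeds 1.645, so the error is at most 0.050. Under the fixed split it is 0.025.

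**3. Power.** Give each statistic mean δ = 1.960 + z(stated power), which is 2.305, 3.165 and 3.903 for the three effects. Write P(a, b) for the chance that the first statistic exceeds a and the second exceeds b. With equal effects in both doses:

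- both doses, fixed = P(1.960, 1.960)
- both doses, Holm = 2 × P(1.960, 1.645) − P(1.960, 1.960)
- per arm, Holm = stated power + P(1.960, 1.645) − P(1.960, 1.960)
- at least one dose, either rule = 2 × stated power − P(1.960, 1.960)

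At 3.16 days, P(1.960, 1.960) = .811 and P(1.960, 1.645) = .8474. Holm both-dose power is 2 × .8474 − .811 = .884. Holm per-arm power is .886 + .8474 − .811 = .922. At least one dose is 2 × .886 − .811 = .961.

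| Gain in both doses | Per arm, fixed → Holm | Both doses, fixed → Holm | At least one, either rule |
|---|---|---|---|
| 2.27 days | .635 → .695 | .479 → .599 | .791 |
| 3.16 days | .886 → .922 | .811 → .884 | .961 |
| 3.94 days | .974 → .986 | .953 → .977 | .995 |

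**4. Check without the normal model.** A three-arm simulation of the mechanism in step 1 (6,000 replicates, no underreporting) gives both-dose power of .474 → .601, .818 → .893 and .965 → .983, with the chance of at least one positive dose the same under both rules. With one dose at about 2.27 days and the other at about 3.16 days, the weaker dose goes from .631 to .724 and both-dose power from .593 to .704. Simulated error with one true null is 0.047 under Holm. The statistics correlate at about 0.4 under these alternatives rather than 0.5, and the gains are much the same.

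**The case against.** The strongest reply is that nothing here is wrong. The split controls the error it declares, the three sections agree, and the power table was computed for that same test. The stated target, more than 85% pairwise power at 3.16 days with underreporting bounded by 20%, is met (.873 in the table). The primary hypothesis asks whether buprenorphine can reduce use days; one positive dose answers that, and Holm does not change that probability. No section sets a target for showing both doses. All of this stands, and it limits the point to the second dose.

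There is also a cost. Today every dose claim needs one-sided 2.5%; under Holm the second would need only one-sided 5%. The fixed split also yields matching simultaneous confidence bounds directly, which Holm does not do so simply. This stands as a downside but does not remove the point, because the protocol states no per-dose 2.5% standard apart from the split used to reach 5%.

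The gain is also uneven. It is 2.4 points for both doses at 3.94 days. If only one dose works, its own power can rise by at most 2.5 points, since the null dose must first be falsely rejected. An arm stopped at the futility look leaves the other at 2.5% and brings no gain.

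Two stronger readings are tempting and are not supported. A reader might infer that the tests are mis-sized because the actual error under the global null is 4.5% rather than 5%. That slack comes from the shared control, it is conservative, and Holm leaves it where it is. A reader might also infer that the trial is underpowered for its primary hypothesis. The protocol's own figures do not show that.

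**Conclusion.** The point holds as a missed efficiency. Under the protocol's single stated criterion, one-sided experimentwise 5%, Holm never rejects less than the fixed split and keeps the error at about 4.5% under the global null and at most 5.0% when one dose works. If both doses share the effect, both-dose power rises by 12.0 points at 2.27 days, 7.3 points at 3.16 days and 2.4 points at 3.94 days; per-arm power rises by 6.0, 3.6 and 1.2 points. The chance of at least one positive dose is unchanged.

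The power figures rest on equal effects in both doses, a bivariate normal approximation with correlation 0.5, no underreporting, and no allowance for the futility look. The direction, that Holm never rejects less, needs none of these assumptions. The plan as written is valid and could be kept. The change is worth making because it costs almost nothing.

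**What to change.** Before unblinding, replace the rule in section 10.4 with wording such as: *The smaller of the two one-sided Wilcoxon p-values is tested at 2.5%; if it is rejected, the other is tested at 5% (Holm). The one-sided experimentwise error is 5%. An arm dropped for futility counts as not rejected.* Align sections 2.7 and 10.2. The table in 10.2 can stay, described as pairwise power at the 2.5% level and hence a lower bound for per-arm power under Holm.

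The cost is one sentence and two matching edits, with no change to sample size, conduct or data collection. The amendment should say openly that the second dose may be claimed at one-sided 5%, and how confidence bounds for the two doses will be reported. If the sponsor wants each dose to meet one-sided 2.5% on its own, the fixed split should stay, with that reason stated.

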#### 10.5 Interim Analyses

Given the relatively small sample size, short duration of the study and needs for precise estimation of multiple outcome measures, early termination for efficacy is not planned. Any claim of treatment difference between the active and control treatments will be made after testing at the end of the trial at which time all Type 1 error will be spent.

It may be that accumulating information shows little treatment effect. After endpoint information for half of the planned study sample is available, each buprenorphine treatment arm will be evaluated versus the no-buprenorphine arm. In the absence of observed benefit for the treatment, the treatment arm will be terminated (i.e. the treatment versus placebo contrast must favor the treatment). This stopping rule corresponds to about 20% conditional power under plausible (i.e. 95% confidence limit of current effect estimate) projections of the study result at the time of the analysis. Such termination does not affect type 1 error.

This assessment will be made by the DSMB who will be provided information necessary to make the decision by the unblinded statistician at the NIDA Data and Statistical Center. Only a single interim inspection for futility is planned a priori, and any subsequent inspections would be at the direction of the DSMB.

#### **10.6** Exploratory Analyses

The primary endpoint will be analyzed with the 2 sample Wilcoxon statistic. If the opioid history strata is identified as a significant predictor of cocaine use days with a mean difference >3.0 days, then the primary endpoint will be analyzed with a stratified Wilcoxon test.

The effect in the "high" versus "low" opioid involvement strata is of interest; strata-specific assessment of the primary outcome will be evaluated.

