#### 7.2 Randomization

Immediately following successful induction onto XR-NTX and a final assessment of eligibility, participants will be randomly assigned to one of the three conditions: (BUP4+XR-NTX), (BUP16+XR-NTX) or (PLB+XR-NTX) for 8 weeks of treatment. Random assignment will be on a 1:1:1 ratio to one of three conditions. Randomization will be stratified according to site and opioid use levels according to the following strata:

- High, defined as 1) ever injected an opioid; 2) greater than or equal to 2 years of regular opioid use (per ASI); or 3) opioid use on 20 or more days in the month preceding screening (per TLFB)
- Low, defined as not meeting criteria for high opioid use

The randomization procedure will be conducted in a centralized process through the CTN Data and Statistics Center (DSC), and randomization assignments will not be conveyed to staff or participants. The DSC statistician will generate the randomization schedule using balanced blocks of varying sizes within strata to ensure lack of predictability along with relative equality of assignment across treatment groups. The DSC statistician will review randomization data on a regular basis to ensure that the scheme is being implemented according to plan. A randomization slot, once used, will not be re-allocated.

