#### **10.1.2** Primary Endpoint

The primary endpoint is the number of cocaine use days during the 30-day evaluation period. The evaluation period will be the last 30 days of the active medication period and will end on the day prior to initiation of the taper. Under the protocol schedule this would be days 25 to 54 inclusive. Cocaine use will be measured by self-report, corroborated with thrice-weekly urine drug screens. Scores for individuals who initiate the evaluation period will be included, and those who discontinue participation will have their score at the time of withdrawal scaled to the 30-day evaluation period.

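### Sections 10.3 and 10.6 do not name one primary test: the opioid-use stratum enters the Wilcoxon test only if the observed outcome data trigger it

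*Protocol*

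**What the plan says.** Protocol 10.1.2 defines the outcome: "The primary endpoint is the number of cocaine use days during the 30-day evaluation period". Section 10.3 gives the test without conditions: "The primary endpoint will be analyzed with the 2 sample Wilcoxon statistic". The same section lists adjustment for strata, with gender, age and race, among the additional analyses.

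Section 10.6, headed as exploratory, repeats the sentence on the two-sample test and then adds a condition: "If the opioid history strata is identified as a significant predictor of cocaine use days with a mean difference >3.0 days". When both parts of that condition are met, section 10.6 gives this consequence: "then the primary endpoint will be analyzed with a stratified Wilcoxon test".

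Section 7.2 shows that the factor was fixed by design: "Randomization will be stratified according to site and opioid use levels". The high and low levels are defined from opioid history before randomization.

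Section 10.4 allots the error, "comprised of 2 pairwise 2.5% level one sided tests of the two buprenorphine arms versus the no-buprenorphine arm", but does not say whether those tests are stratified. Section 2.7 gives the total: "for an overall experimentwise 5% Type I error rate".

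**The concern.** The trigger in 10.6 is evaluated on cocaine use days, which is the primary endpoint itself. If 10.6 means what it says, the form of the confirmatory test is settled only after the outcome has been observed. If the heading of 10.6 governs instead, the stratified test is supportive and 10.3 stands alone. The text supports both readings, so a borderline trial could end with two p-values, each with a claim to be primary.

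There is no need to wait for the data. Opioid-use level was judged important enough to stratify randomization, and it is known for every participant at baseline. A test that ignores a prognostic stratification factor tends to be conservative and to lose power.

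**Working it through.** **Inputs from the protocol.** 100 randomized per arm, with 5% lost before the evaluation period, leaves 95 per arm and 285 in all. Daily use is beta-binomial (0.45, 1) over 30 days. There are two one-sided tests at 2.5%. The trigger is a significant stratum effect and a mean difference above 3.0 days.

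**Assumptions not in the protocol.** The share of the high stratum (50%, also 70%), the true stratum difference (0 to 6 days), a 5% t-test as the pre-test, and the way the treatment effect enters.

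**The plan's own figures.**
- Mean: 30 × 0.45/1.45 = 9.31.
- Variance: 30 × 0.3103 × 0.6897 × (1.45 + 30)/(1.45 + 1) = 82.4, so the SD is 9.08. Both match section 10.2.
- Error: 2 × 0.025 = 0.05, as stated.

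**How sharp the trigger is.** With equal strata the standard error of the stratum difference is 9.08 × √(1/142.5 + 1/142.5) = 1.08 days. The 5% significance limit is 1.96 × 1.08 = 2.1 days, so the 3.0-day threshold (about 2.8 standard errors) is the binding condition.

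**Simulated one-sided error per comparison, no drug effect** (three arms, 95 per arm, equal strata, 6,000 trials, simulation error about 0.002):

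| True stratum difference (days) | Trigger fires | Unstratified | Always stratified | Switch rule |
|---|---|---|---|---|
| 0 | 0.005 | 0.0257 | 0.0243 | 0.0258 |
| 2 | 0.171 | 0.0252 | 0.0262 | 0.0255 |
| 3 | 0.498 | 0.0240 | 0.0252 | 0.0243 |
| 4 | 0.815 | 0.0230 | 0.0262 | 0.0258 |
| 6 | 0.996 | 0.0185 | 0.0243 | 0.0243 |

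With 70% in the high stratum, the rule gives 0.024 to 0.027 and the unstratified test at 6 days gives 0.017. Over both comparisons and both shares, the rule's overall error is 0.041 to 0.050. Applying the trigger pair by pair gives the same picture (0.0237 to 0.0243 at 0, 3 and 6 days).

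**Simulated power for one arm, average effect 3.16 days** (proportional reduction of use, no dropout, 3,000 trials, standard error about 0.009):

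| True stratum difference (days) | Unstratified | Always stratified | Switch rule |
|---|---|---|---|
| 0 | 0.516 | 0.515 | 0.516 |
| 2 | 0.513 | 0.516 | 0.514 |
| 3 | 0.513 | 0.534 | 0.525 |
| 4 | 0.500 | 0.530 | 0.529 |
| 6 | 0.484 | 0.555 | 0.555 |

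The rule's largest shortfall against always stratifying is 0.534 − 0.525 = 0.009. The unstratified test's largest shortfall is 0.555 − 0.484 = 0.071.

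**Sensitivity to the effect model.** At a 6-day stratum difference:
- A second run under proportional reduction, 96 per arm, gave 0.469 unstratified against 0.546 stratified, a loss of 0.077.
- A run with the planned dropout and scaling gave 0.871 against 0.894, a loss of 0.023.
- A model in which a fraction of treated participants become abstinent gave 0.904 against 0.898, so no loss.

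Absolute power varies because the protocol does not say how the effect entered its own simulation. For 3.16 days and no underreporting it states 0.886; the models tried span 0.52 to 0.92.

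**The case against.** The strongest reply is that the power argument does not touch the rule. Section 10.6 moves to the stratified test when the stratum matters, so the loss of the always-unstratified test is what the rule prevents. That stands: rule and always-stratified differ by at most about 1 point of power. In a separate check they reached different conclusions in at most 2.2% of trials, and in at most 0.2% under the null. In that check, at a 3-day stratum difference, the stratified and unstratified tests disagreed in 0.4% of null trials and in 1.4% to 3.3% with a 3.16-day effect. The trigger may fire like a coin toss there, but it seldom decides the trial.

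A coherent reading also exists: 10.3 and 10.4 set the primary analysis, 10.3 calls strata adjustment additional, and 10.6 is exploratory. That is possible, but the conditional sentence in 10.6 is worded as the analysis of the primary endpoint, not as a supplement. The missing level and model for the pre-test could properly be left to a statistical analysis plan, and the point does not rest on them.

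A reader might infer two stronger charges. One is that a data-driven choice of test inflates type I error; the simulations show none beyond simulation error. The other is that the trigger needs unblinded data. The documents do not say so: a stratum difference in use days can be computed pooled over arms without treatment codes.

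Finally, stratifying by opioid level alone does not fully match the randomization, which also used site. That is fair, and the fix has to address it.

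**Conclusion.** The point holds as a lack of one fixed primary test, with a modest statistical cost. Sections 10.3 and 10.6 do not agree on the test, and 10.6 ties the choice to observed outcome data for a factor already built into the randomization. The type I error is sound under the rule, and the rule's power is within about 1 point of always stratifying. The avoidable loss applies if 10.3 governs. There, one-sided error falls to about 0.017 to 0.019 at a 6-day stratum difference, and power falls by anything from nothing to about 7 to 8 points. A reader might attach that loss to the switch rule; it belongs to the unstratified test used throughout.

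These sizes rest on assumed stratum shares, assumed stratum differences, a t-test as the pre-test and an assumed effect model. When the strata do not differ, stratifying costs nothing visible (0.515 against 0.516). This is a free improvement.

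**What to change.** Delete the conditional sentence in 10.6. In 10.3, 10.4 and 10.6 name one primary test: the Wilcoxon test stratified by the opioid-use level recorded at randomization (van Elteren), applied to each buprenorphine arm against control at the one-sided 2.5% level, whatever the observed stratum difference. Keep the unstratified two-sample test as a sensitivity analysis. The stratum-specific assessments in 10.6 can stay exploratory.

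State how site is handled. With 10 to 12 sites and 100 per arm there are about 8 to 10 participants per arm per site, or on average 4 to 5 once split by opioid level. Leaving site out of the primary test and examining it separately may be reasonable, but the choice should be written down.

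The cost is wording only: no change to sample size, data collection or error allocation.
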